Via participants’ Ontario Health Insurance Plan (OHIP) number, we will link to the ICES provincial administrative database to obtain participants’ vaccine status, and rates of SARS-CoV-2 infection, hospitalization and death, over the study period. [38, 39]. Unique to the exit survey, study participants will be asked about their satisfaction with the intervention. A process evaluation will be conducted to assess quality and delivery of the study intervention. The resource navigator will track the number, duration and focus of the 1:1 sessions per participant at the end of each individual session using a Process Evaluation- Intervention Tracking Form (Appendix Q). Participant experiences, suggestions for improvement and planning for sustainability will be collected via individual interviews with the resource navigator. A sample of

Evaluating the impact of resource navigators to support long-term care and retirement home staff during and beyond COVID-19

Principal Investigators: Drs. [name] and [name]

Research ethics protocol

Version Dates: Sept 7th, 2022

Version Number: 2

control (n=8-10) and intervention (n=8-10) participants will be interviewed. We will purposively sample the group, with an aim to reflect diversity in gender, age, race and other PROGRESS-plus characteristics

13. Participant Timeline

As noted above, the primary and secondary outcomes will be assessed using a multi-measure baseline and exit survey. Baseline surveys will be conducted 0-30 days after randomization and exit surveys will be conducted at 6 months (182 days) after the randomization date.

Process evaluation data will be collected throughout the duration of the intervention (from 0 days after randomization until the end of intervention (182 days)).

Post-intervention exit interviews will then be conducted at approximately 6-7 months (182-213 days) after the randomization date. These interviews will include a subsample of 8-10 participants from the intervention arm and 8-10 participants from the control arm of the study. See Figure 1 for flow of participants. Note: this will be a rolling recruitment.

Evaluating the impact of resource navigators to support long-term care and retirement home staff during and beyond COVID-19

[figure not shown]
Principal Investigators: Drs. [name] and [name]

Research ethics protocol

Version Dates: Sept 7th, 2022

Version Number: 2

Figure 1. Flow of Participants

14. Sample Size

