Due to the nature of the intervention, neither participants nor researchers will be blinded to the study arm; however, statisticians conducting the outcome analysis will be blinded to which arm participants were assigned. PSWs and other support service staff in the same long-term care and retirement home may be randomized to different study arms, which may cause contamination; however, this is unlikely since those in the control arm will not have access to the navigators.

Evaluating the impact of resource navigators to support long-term care and retirement home staff during and beyond COVID-19

Principal Investigators: Drs. [name] and [name]

Research ethics protocol

Version Dates: Sept 7th, 2022

Version Number: 2

17b. Emergency Unblinding

Since direct study participants and researchers will not be blinded throughout the duration of the study, unblinding procedures will not be required or necessary for the purposes of this trial

Methods: Data collection, management, and analysis

18. Data Collection Methods

18a. Data Collection Methods

Data will be collected by the Knowledge Translation Program, Li Ka Shing Knowledge Institute, Unity Health Toronto (KTP-UHT). Baseline and exit surveys will be administered online via REDCap.

The study will use the Dillman Total Design Method (follow up at 1, 3, 7, 10 weeks) to increase survey responsiveness. [40] Participants who indicate interest and meet study criteria will be asked to complete a baseline survey at the beginning of the study (0 weeks). If they do not respond immediately, they will receive reminder emails at 1, 3, 7 and 10 weeks. At the 6-month mark, after study completion (26 weeks), participants will be asked to complete an exit survey. If they do not respond immediately, they will also receive reminder emails at 1, 3, 7 and 10 weeks. However, based on whether there are delays in the ability to recruit participants due to a lack of response to recruitment emails and reminders, there is a possibility that the surveys will not take place at the exact times noted above. If this occurs, we will make sure to note this in our limitations. All survey questions have been reviewed by the steering committee for acceptability, clarity of language and feasibility of format (e.g., mobile friendly access).

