As mentioned above data will be collected using a baseline and exit survey in addition to an exit interview. Refer to table 1 for a description of the data that will be collected for each data collection method.

Table 1

Data Collection Tool	Objective	Number of participants	Data Collection Time Point	Factors Assessed	Measures used
Baseline Survey	
• Outcome evaluation• Demographic information	
• up to 154 participants (77 per arm)	
• At 0 month, Study Coordinator and Assistant will collect Baseline survey data	
• Wellbeing• PROGRESS-Plus factors (gender, sex, religion, education, socioeconomic)	
• Personal Wellbeing Score (Primary Outcome)• Demographic questionnaire-PROGRESS-Plus

Evaluating the impact of resource navigators to support long-term care and retirement home staff during and beyond COVID-19

Principal Investigators: Drs. [name] and [name]

Research ethics protocol

Version Dates: Sept 7th, 2022

Version Number: 2

				status, and social capital) 
 • Knowledge • Access to supports • Use of wellness supports 	Framework and OHIP number 
 • Maslach Burnout Inventory • Likert scale questions evaluating knowledge, access to and use of wellness supports
Field Notes/Logs	
 • Process evaluation /Implementation quality 	
 • tracking data for 77 participants 	
 • At 0-6 months, Resource Navigator will collect field notes during intervention 	
 • Implementation quality 	
 • Number of 1:1 resource navigation sessions • Duration of 1:1 resource navigation • Focus of 1:1 resource navigation sessions • adoption (e.g., uptake, utilization, intention to try) of the materials and resources provided

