Exit Survey	
 • Outcome evaluation • Demographic information 	
 • up to 154 participants (77 per arm) 	
 • At 6 months, Study coordinator and Assistant will collect Exit Survey data after completion of intervention 	
 • Wellbeing • PROGRESS-Plus factors (gender, sex, religion, education, socioeconomic status, and social capital) • Knowledge • Access to supports • Use of wellness supports • Satisfaction with the intervention 	
 • Personal Wellbeing Score (Primary Outcome) • Demographic questionnaire-PROGRESS-Plus Framework and OHIP number (if not collected at baseline) • Maslach Burnout Inventory • Likert scale questions evaluating knowledge, access to and use

Evaluating the impact of resource navigators to support long-term care and retirement home staff during and beyond COVID-19

Principal Investigators: Drs. [name] and [name]

Research ethics protocol

Version Dates: Sept 7th, 2022

Version Number: 2

					of wellness supports
Exit Interview	
 • Outcome evaluation • Process evaluation /Implementation quality 	
 • 8-10 participants from intervention arm • 8-10 participants from control arm 	
 • At 6-7 months, Research coordinator will collect interview feedback post intervention 	
 • Barriers and facilitators • Wellbeing • Participant experiences • Suggestions for improvement • Planning for sustainability • Implementation quality 	
 • Interview questions
ICES provincial administrative database	
 • Outcome evaluation 	
 • up to 154 participants (77 per arm) (data linkage using OHIP#) 	
 • At 6-7 months, Study coordinator and Assistant will use OHIP number to link administrative data 	
 • Vaccine status • Rates of SARS-CoV-2 infection • Hospitalization • Death 	
 • ICES provincial administrative database fields

18b. Retention

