All interested potential participants (PSW's and other support workers in long-term care and retirement homes) will receive a link to the pre-screening survey (Appendix C) to determine eligibility. If eligible, participants will receive a pre-screening confirmation email (Appendix D) which will contain the link to the study information sheet and informed consent process (Appendix E). Contact information for members of the study team will also be provided. Participants will be encouraged to reach out with any questions. Participants will be asked to review all the study details and provide consent by selecting one of the two consenting statements at the end of the survey. Participants will then be emailed their unique study ID and the link to the baseline survey. The study team will reach out again at 6 months with a link to complete an exit survey.

Consent at enrollment includes participating in:

- 1:1 sessions with the resource navigator and access to educational resources (if assigned to intervention arm. Access to educational resources only (if assigned to the control arm)
- Participation in the baseline survey and exit survey. Participants will be assigned to either an intervention or control arm and will be invited by email (Appendix F - initial email, G - reminder email) to complete the baseline survey, a demographic questionnaire (Appendix H). The baseline survey will be used to select a diverse participant group (purposive sample). Participants will be given the opportunity to consent and provide their OHIP number for data linkage. An invitation email (Appendix I – initial email, J – reminder email) will also be sent to complete the exit survey (Appendix K) where they will also be given the opportunity to provide their OHIP number for data linkage if not provided during the baseline survey.
- Participants' response to any questionnaire will be kept confidential. Participants will be provided with a unique study ID (Appendix F, I) to complete the baseline and exit survey

Evaluating the impact of resource navigators to support long-term care and retirement home staff during and beyond COVID-19

Principal Investigators: Drs. [name] and [name]

Research ethics protocol

Version Dates: Sept 7th, 2022

Version Number: 2

(Appendix H, K) so that their responses remain de-identified. Identifiers and unique study IDs will be recorded on a master linking log (Appendix L).

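### The OHIP number needed for ICES linkage is requested after open-label allocation, so who is linked can differ by arm.

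*Combined protocol and SAP*

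**What the plan says.** **Order of events.** Section 13: "Baseline surveys will be conducted 0-30 days after randomization and exit surveys will be conducted at 6 months (182 days) after the randomization date". Section 26a gives the same order: "Participants will be assigned to either an intervention or control arm and will be invited by email" to the baseline survey. Section 18a sends baseline reminders at 1, 3, 7 and 10 weeks.

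**Masking.** Section 17a: "neither participants nor researchers will be blinded to the study arm". Only the statisticians analysing outcomes are blinded.

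**Linkage request.** Section 26a: "Participants will be given the opportunity to consent and provide their OHIP number for data linkage". It then describes the exit survey, "where they will also be given the opportunity to provide their OHIP number for data linkage if not provided during the baseline survey". Table 1 agrees: its baseline row lists "Framework and OHIP number" among the measures, and its exit row lists "OHIP number (if not collected at baseline".

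**A second account.** Section 29 directs the linkage request to participants who complete the baseline survey, the intervention and the exit survey.

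**De-identification.** Section 26a has participants use a study ID in both surveys "so that their responses remain de-identified". Sections 19, 26a and 27 place identifiers and study IDs on a master linking log.

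**Analysis.** Section 20a plans t-tests between arms. Section 20b names no additional analysis, and section 20c leaves the missing-data plan to be developed. No passage describes linkage rates by arm or a comparison of linked with unlinked participants.

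**The concern.** Randomisation makes the two arms comparable as randomised. It does not make comparable the subset who later choose to hand over a health-card number. Here that choice is made by people who know their arm and, at exit, after six months with or without a navigator. If navigator contact changes willingness to share the number, and willingness is related to the outcome (attitude to vaccination is an obvious candidate), the linked arms differ even when the intervention does nothing.

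At stake are the four ICES outcomes. Linkage that was never obtained cannot be restored at analysis, and the plan has no provision for it.

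A smaller matter is that Table 1 lists a direct identifier among the measures of the same surveys whose answers are said to be de-identified.

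**Working it through.** **1. Timing, reading the sections together.**

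| Step | When | Source |
|---|---|---|
| Enrolment consent | Before randomisation | 16c, 26a |
| Allocation, open to participants | Day 0 | 16c, 17a |
| First OHIP request (baseline survey) | Days 0-30 | 13, Table 1 |
| Last baseline reminder | 10 weeks (70 days) after the invitation | 18a |
| Second OHIP request (exit survey) | Day 182 | 13, 26a, Table 1 |

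No request for the number is described before day 0. A baseline response to the last reminder could come 70 - 30 = 40 days or more after the 30-day window closes.

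**2. Section 29 does not remove the problem.** Completing the surveys and the intervention is itself a post-allocation event. The plan does not say what completing the intervention means for controls, who have no navigator sessions. Read literally, a request limited to people who finish the exit survey could not capture a death before exit.

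**3. Outcomes affected.** Section 12 and Table 1 take vaccine status, infection, hospitalisation and death from ICES. The research question in section 6a calls infection and hospitalisation self-reported, but Table 1 lists no survey item for them, so I follow section 12 and Table 1. The Personal Wellbeing Score does not depend on linkage.

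**4. Possible size.** The plan gives no linkage rate to reproduce. I take only 77 per arm from it (64 × 1.20 = 76.8, sized for the wellbeing score). Every rate below is assumed, and the true rates are equal in both arms.

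*Illustration A, vaccination.* Let 25% of staff be hesitant, with 10% of them up to date, against 63.3% of the others. The true share is 0.25 × 0.10 + 0.75 × 0.633 = 50%. Others link at 80% in both arms. Hesitant staff link at 30% in the control arm and 60% in the navigator arm.

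- Control: linked 0.60 + 0.075 = 67.5% (52 people); up to date among linked (0.380 + 0.0075)/0.675 = 57.4%.
- Navigator: linked 0.60 + 0.15 = 75% (58 people); up to date among linked (0.380 + 0.015)/0.75 = 52.7%.
- False difference: 4.7 points. Standard error: √(0.574 × 0.426/52 + 0.527 × 0.473/58) = 9.5 points, so the artefact is about half a standard error.

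This applies the navigator effect to every request. If only half of the 30-point excess arises, hesitant navigator-arm staff link at 45%. Their arm's linked share is then (0.380 + 0.01125)/0.7125 = 54.9%, and the gap is 2.5 points. With no excess the gap is 0.

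*Illustration B, a generic event with true rate p.* The intervention arm links at 80% whatever the outcome. Controls link at 60% without the event and at q with it. The observed control rate is pq/[pq + 0.6(1 - p)]; the observed intervention rate is p.

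| p | q = 50%: control rate (gap) | q = 40%: control rate (gap) |
|---|---|---|
| 10% | 8.5% (1.5 points) | 6.9% (3.1 points) |
| 20% | 17.2% (2.8 points) | 14.3% (5.7 points) |
| 30% | 26.3% (3.7 points) | 22.2% (7.8 points) |

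About 42-45 controls and 62 intervention participants would be linked. For the largest gap the standard error is √(0.222 × 0.778/41.6 + 0.30 × 0.70/61.6) = 8.7 points, so 7.8 points is 0.9 of a standard error. If linkage depends on neither arm nor outcome, the gap is 0. The direction follows from the assumptions.

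**The case against.** **Linkage consent may be taken at enrolment.** The sentence offering it stands in the list of what enrolment consent covers, and the consent form (Appendix E) is not shown. This stands: the text does not prove that consent to linkage is given after allocation. But the number is what makes linkage possible, and section 26a and Table 1 both tie it to the surveys.

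**The navigator has little time to act on the first request.** The timeline table puts the baseline survey in June-July and the intervention from August, and exit is only a fallback. This largely stands, and it is why numbers first given at exit are the main route. Rolling recruitment and reminders to 10 weeks leave some overlap at baseline, and knowledge of the arm is present from the start.

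**The sizes are assumed and small against the noise.** This stands. They show a mechanism and do not estimate a bias.

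**De-identification.** A reader might infer that the survey answers are not de-identified at all. The documents do not support that. A master linking log is described in three sections, access to identifying information is limited to the study team, Table 1 lists measures and not database forms, and Appendices H, K and L are not shown. What remains is that no step separating the number from the answers is described.

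**The primary outcome.** A reader might also infer that a health-card question reduces candour or completion on the wellbeing score. Nothing in the documents supports this, and both arms receive the same request.

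**Conclusion.** The point holds for the ICES outcomes. Under section 26a with Table 1, or under section 29, inclusion in the linked comparison is decided after open-label allocation and can differ by arm. The plan has no safeguard and does not report linkage by arm.

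The size is unknown. Under the assumed rates above it runs from 0 to about 8 points in either direction, in every case less than one standard error. These are secondary outcomes on which the sample size was not based. Any real bias requires linkage to depend on both arm and outcome, which is plausible but not shown. The case for acting is that this selection route is avoidable at low cost beforehand and cannot be undone afterwards.

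**What to change.** 1. Ask for optional linkage consent and the OHIP number with the enrolment consent, before randomisation, and state that refusal does not affect eligibility. A choice made before allocation cannot depend on the arm.
2. Reconcile sections 26a and 29 so that one rule says who is asked and when.
3. Base the main ICES comparison on people who consented before allocation. Report linkage rates by arm. Use numbers first given at exit only in a sensitivity analysis.
4. Record the number on an identifier form kept with the master linking log and remove it from the survey measures in Table 1, so that the de-identification statement in section 26a holds as written.

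**Cost.** One question moves to another form, and the consent sheet is amended. One more sensitive question at enrolment, even if optional, could deter a few people. The main ICES analysis will have somewhat fewer linked participants. For scale, an assumed 20% v 10% comparison (two-sided 5%) has 41% power with all 77 per arm linked, 34% at 80% linkage and 27% at 60%. The loss is real, but power is low even with full linkage.
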